4.4 Management of Toxicities and Dosage Modifications

Suggested doses of supportive care therapies are provided; however, adjustment of the dosages based on the patient's clinical condition or each institution's standard of care is permitted.

4.4.1 Management of Nonhematologic Toxicities

Adverse events may be treated with concomitant medications, as deemed clinically indicated by the Principal Investigator. All concomitant medications must be recorded in the source and on the appropriate CRF.

Adverse events that are moderate to severe in intensity (see [Appendix C](#) for toxicity grading) and considered possibly or probably related to study drug treatments may result in the delay or termination of study treatment in affected patients.

4.4.1.1 Hyperkalemia and Tumor Lysis Syndrome

Tumor lysis may occur as part of initial cytoreductive therapy. The most extreme form, known as Tumor Lysis Syndrome (TLS), is characterized by hyperkalemia, hyperuricemia, hyperphosphatemia, increased lactate dehydrogenase (LDH), coagulopathy, and a potential cytokine release syndrome.

Mandatory IV hydration with 0.45% NaCl (or similar hydration fluid per institutional standard) sterile solution at 100 cc/hour for at least 10 hours prior to initiation of the first dose of chemotherapy during Induction (optional for subsequent cycles including Reinduction). If, by Day 4, there is no evidence of tumor lysis syndrome, the hydration rate can be reduced to a maintenance level.

Diligent monitoring of urine output frequently to ensure that fluid output equals fluid input. If input is greater than output by 10%, administration of diuretics is encouraged. Replacement of excessive fluid losses, including from diarrhea, should be done unless otherwise clinically indicated.

- Mandatory allopurinol orally each day of dosing for first cycle to be started at same time as initiation of IV hydration
- Mandatory oral phosphate binder to be started at the same time as initiation of IV hydration, unless contraindicated.
- Evaluation of laboratory indicators of tumor lysis syndrome (TLS) during Induction therapy. Evaluation of laboratory indicators of TLS may be adjusted for Reinduction and Consolidation therapy based on extent of tumor burden.
 - Tumor lysis laboratory evaluations ('tumor lysis labs') include electrolytes (sodium, potassium, chloride, and carbon dioxide) as well as creatinine, calcium, lactate dehydrogenase (LDH), uric acid, and phosphorus levels.
 - For patients **at high risk** for TLS including those with risk scores of ≥ 2 according to the table in *Appendix F*, those with monocytic leukemia phenotype, or those with a history of FLT3 positive AML:
 - Obtain a STAT serum potassium at end of alvocidib infusion
 - Strongly recommend serum potassium at 2 hours post end of alvocidib infusion as best practice
 - Obtain full TLS panel at 4 hours post end of alvocidib infusion
 - If evidence of clinically meaningful TLS, obtain TLS panel every 2 hours during the first 24 hours post end of alvocidib infusion (LDH levels are recommended to be assessed at least once every 24 hours).

- If no evidence of clinically meaningful TLS, obtain TLS panel every 4 hours during the first 24 hours post end of alvocidib infusion (LDH levels are recommended to be assessed at least once every 24 hours).
- If, after the first 24 hours post end of alvocidib infusion, there is no evidence of TLS, obtain TLS panel approximately every 6 hours for the remainder of alvocidib treatment and then every 12 hours after completion of alvocidib and during daunorubicin and cytarabine (LDH levels are recommended to be assessed at least once every 24 hours).
- Monitor fibrinogen levels at baseline and then as clinically indicated.
- Patients who are determined to be at intermediate- or high-risk for TLS should be considered for rasburicase prophylaxis according to institutional standards
- For patients **NOT at high** risk for TLS:
 - During the first 24 hours - Monitor tumor lysis labs at the start of alvocidib and approximately every 4 hours. Laboratory studies during this period should be run as a “STAT” to ensure the results are available in a timely manner.
 - If no evidence of TLS during first 24 hours, then monitor tumor lysis labs approximately every 6-8 hours for the remainder of alvocidib treatment and then every 12 hours after the completion of alvocidib and during cytarabine and daunorubicin.
 - Monitor fibrinogen levels at baseline and then as clinically indicated.

Risk of TLS and Guidelines for Management of High Risk Patients

TLS management during treatment with alvocidib was implemented in previous studies, which included medical prophylaxis for hyperuricemia, as well as aggressive monitoring and management of hyperkalemia and other biochemical laboratory abnormalities. Rapid development of hyperkalemia has been of particular concern in earlier studies. While these guidelines are not necessarily consistent with specific standard recommendations for the treatment of TLS, they are recommended based on previous experience with the treatment of patients with alvocidib. These measures resulted in a lower incidence of TLS without adverse outcomes.

For this reason, investigators are encouraged to follow the recommended guidelines below but may follow your own institution's protocols in determining the best treatment for your patients.

- If potassium levels are increasing to >4.0 mEq/L, patients should receive a 30 gm dose of sodium polystyrene sulfonate, unless there are other likely causes of hyperkalemia other than TLS or contraindication to its use.
- If potassium levels rise to >5.0 mEq/L, in addition to the 30-gm dose of sodium polystyrene sulfonate, patients should also receive 10 units of IV rapid-acting insulin and 25 gm (one ampule) of IV dextrose 50%, unless there are other likely causes of hyperkalemia other than TLS or contraindication to its use.
- If potassium levels rise to >5.5 mEq/L, patients should be considered for emergent intermittent or continuous dialysis.
- Calcium supplementation should only be given for symptomatic hypocalcemia in this setting to avoid renal precipitation of calcium phosphate crystals.
- Patients who develop clinical evidence of cytokine release syndrome or who have hyperkalemia requiring dialysis will receive immediate steroid therapy with an equivalent of at least 20 mg of IV dexamethasone.

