4.3.2 Study Drug Administration

Induction – Alvocidib and 7+3

- *Days 1, 2, 3:* Alvocidib at a starting dose of 20 mg/m² as a 30-minute (±10 minutes) IV bolus followed by 30 mg/m² administered as a 4-hour (±15 minutes) IV infusion (this is the starting dose for Cohort 1; see [Table 3](#) for assigned alvocidib doses per treatment cohort)
- *Day 4:* Drug-free day
- *Days 5, 6, 7: (7+3)* Daunorubicin 60 mg/m² via IV bolus of up to 15 minutes' (±5 minutes) duration each day followed immediately by;
- *Days 5, 6, 7, 8, 9, 10, 11:* Cytarabine 100 mg/m²/day via continuous 24-hour IV infusion (±2 hours for infusion duration each day)

Reinduction – Alvocidib and 5+2

Patients **with** evidence of residual leukemia defined as >5% bone marrow blasts plus >10% cellularity, based on the Day 14 (±3 days) bone marrow will be eligible to start a second induction cycle (ie, Reinduction) with alvocidib plus 5+2. The second induction cycle with alvocidib plus 5+2 will be allowed per investigator discretion.

- *Days 1, 2, 3:* Alvocidib at same dosage as during Induction
- *Day 4:* Drug-free day
- *Days 5, 6: (5+2)* Daunorubicin 45 mg/m²/day via IV bolus of up to 15 minutes' (±5 minutes) duration each day followed immediately by;
- *Days 5, 6, 7, 8, 9:* Cytarabine 100 mg/m²/day via continuous IV infusion (±2 hours for infusion duration each day)

Consolidation – HiDAC

Consolidation therapy will consist of high-dose cytarabine (HiDAC) which may be initiated at the time of hematologic recovery or within 90 days of recovery. Consolidation therapy may start before complete hematologic recovery after discussion with the Medical Monitor. It is not anticipated that all patients will undergo Consolidation therapy.

- *Days 1, 3, 5:* HiDAC 3 gm/m² IV every 12 hours (1.5 gm/m² in patients aged 60 to 65 years) (ie, a total of 6 doses over the 3-day regimen); lower starting dose may be permitted at the discretion of the Investigator and after discussion with the Medical Monitor

Patients who plan to receive chemotherapy-based consolidation should get a minimum of two cycles of Consolidation up to a maximum of four cycles. Patients proceeding to stem cell transplant for Consolidation should get one cycle of Consolidation, if possible, to ensure disease stability while transplant plans are being made.

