5.2.3 Induction – Daily during Hospitalization for Chemotherapy

Perform the following procedures daily (or more frequently if clinically indicated) while patients are hospitalized for chemotherapy administration:

- Collect blood for evaluation of laboratory parameters (Appendix D):
 - Hematology
 - Bilirubin, creatinine, alanine aminotransferase (ALT), aspartate aminotransferase (AST), alkaline phosphatase (ALP)
 - Tumor lysis labs as outlined in Section 4.4.1.1 (or more frequently if clinically indicated)
 - Fibrinogen level (as clinically indicated)
- Monitor urine output frequently to ensure that it equals fluid input. If input is greater than output by 10%, administration of diuretics is encouraged. Replacement of excessive fluid losses, including from diarrhea, should be done unless otherwise clinically indicated.
- Assess for AEs
- Record only those medications (prescription, nonprescription, nutritional supplements) administered in conjunction with an AE.

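### On Day 1, high-risk patients without evident TLS have no required full TLS panel from baseline until about 8.5 h, while lower-risk patients have STAT full panels at about 4 h and 8 h

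*Protocol*

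**What the plan says.** All patients have a full set of tumor lysis labs just before the first dose (Protocol 5.2.1.2). Alvocidib is then given as a "30-minute (±10 minutes) IV bolus followed by" a second dose "administered as a 4-hour (±15 minutes) IV infusion" (Protocol 4.3.2).

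Protocol 4.4.1.1 sets two sampling schedules.

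- **High risk** (Appendix F score of 2 or more, monocytic phenotype, or a history of FLT3-positive AML): "Obtain a STAT serum potassium at end of alvocidib infusion"; a potassium 2 hours later that is strongly recommended but not required; then "Obtain full TLS panel at 4 hours post end of alvocidib infusion". Further panels are 4-hourly up to 24 hours after the infusion if TLS is not evident. Otherwise: "If evidence of clinically meaningful TLS, obtain TLS panel every 2 hours during the first 24 hours post end of alvocidib infusion".
- **Not high risk:** "During the first 24 hours - Monitor tumor lysis labs at the start of alvocidib and approximately every 4 hours". All labs in that period are to be run STAT, "to ensure the results are available in a timely manner".

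Sections 5.2.2 (Day 1 dosing) and 5.2.3 (daily during chemotherapy) refer back to 4.4.1.1 and set no other Day 1 panel times. Section 5.2.3 does allow labs "or more frequently if clinically indicated".

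**The concern.** The two schedules run on different clocks, and over the first hours of Day 1 this puts the risk tiers in the wrong order. The tier in which TLS is most expected waits about twice as long for its first required full panel.

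Section 4.4.1.1 describes TLS by raised uric acid and phosphate as well as potassium, and SAP 7.10.3 requires at least two of uric acid, potassium, phosphorus and calcium for laboratory TLS. A potassium-only draw cannot establish laboratory TLS by itself. It is also the only required laboratory result before about 8.5 h that could prompt the move to 2-hourly panels. An early rise in phosphorus, uric acid or creatinine, or an early fall in calcium, would be measured in a high-risk patient only if someone ordered more than the protocol requires.

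The STAT instruction is also reversed. It covers every first-24-hour lab in the lower tier, but only the end-of-infusion potassium in the high-risk tier.

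The background makes this worth correcting. Protocol 2.8 states that alvocidib has not been given clinically with cytarabine and daunorubicin before, and cites tumor lysis and possible renal failure as the reason for aggressive prophylaxis. TLS of any grade occurred in 19 of 45 patients (42%) in one earlier study of alvocidib with cytarabine and mitoxantrone (2.6.2.1). Rates in the two later studies of newly diagnosed patients were 8% to 9% (2.6.2.2, 2.6.2.3).

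**Working it through.** The plan states no figure for this interval, so there is none to reproduce. Times are hours from the start of the bolus. I assume no pause between bolus and infusion, take the approximate 4-hourly interval as exactly 4 h, and take the high-risk patient as having no TLS evident before the first full panel.

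**Clock times**

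- End of infusion = 0.5 + 4 = 4.5 h. Shortest: 20 + 225 = 245 min = 4.08 h. Longest: 40 + 255 = 295 min = 4.92 h.
- First required full high-risk panel = 4.5 + 4 = 8.5 h (8.08 to 8.92 h). A pause between bolus and infusion would add directly to this.

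| | High risk | Not high risk |
|---|---|---|
| Full panel, pre-dose or at start | 0 | 0 |
| Potassium only, required, STAT | 4.5 | – |
| Potassium only, recommended | 6.5 | – |
| Later full panels, first-24-hour schedule | 8.5, 12.5, 16.5, 20.5, 24.5, 28.5 | 4, 8, 12, 16, 20, 24 |
| Of these, labelled STAT | 0 of 6 | 6 of 6 |

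Before 8.5 h there are two full post-dose panels in the lower tier and none in the high-risk tier.

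**Mean wait from onset to the next required measurement**

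The documents give no TLS onset times, so onset is taken as uniform over a stated window. Within each stretch, the mean wait is the average of the waits at its two ends.

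Onset over 0 to 8.5 h:

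- Phosphorus, uric acid, calcium, creatinine, high risk: 8.5/2 = 4.25 h (maximum 8.5 h).
- Same analytes, lower risk: (4×2 + 4×2 + 0.5×3.75)/8.5 = 17.875/8.5 = 2.10 h (maximum 4 h).
- Potassium, high risk: (4.5×2.25 + 4×2)/8.5 = 18.125/8.5 = 2.13 h. With the recommended 6.5 h draw: (4.5×2.25 + 2×1 + 2×1)/8.5 = 14.125/8.5 = 1.66 h. Lower risk: 2.10 h, as above.
- High risk with a full panel at 4.5 h: all required analytes follow the required potassium times, so 2.13 h (maximum 4.5 h).

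**Where the difference arises (non-potassium analytes)**

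- Onset during dosing, 0 to 4.5 h: high risk 8.5 − 2.25 = 6.25 h; lower risk (4×2 + 0.5×3.75)/4.5 = 9.875/4.5 = 2.19 h; high risk after the change 4.5/2 = 2.25 h.
- Onset after dosing, 4.5 to 8.5 h: high risk 4/2 = 2.0 h; lower risk (3.5×1.75 + 0.5×3.75)/4 = 8/4 = 2.0 h. No difference.
- Onset over 0 to 24 h: high risk (8.5×4.25 + 12×2 + 3.5×2.25)/24 = 68/24 = 2.83 h; lower risk 2.0 h.

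**The case against.** The strongest defence is that a potassium-first schedule is deliberate. Section 4.4.1.1 singles out rapid hyperkalemia as the main concern from earlier alvocidib studies, and its numeric treatment triggers (above 4.0, 5.0 and 5.5 mEq/L) are all for potassium. An earlier phosphorus or uric acid result would change no protocol-specified treatment, only the frequency of panels. That step-up depends on clinically meaningful TLS, which urine output or bedside findings could also show in a hospitalised patient. Hydration and allopurinol are mandatory, as is a phosphate binder unless contraindicated, and rasburicase is to be considered. Extra labs are allowed. After the first panel, high-risk sampling is at least as frequent as in the lower tier, and only the high-risk tier has a 2-hourly step-up.

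The size of the effect also depends on the onset window. Over 0 to 24 h the difference in mean wait is about 0.8 h, and for onset after the infusion ends it is nil. The STAT comparison counts labels; it does not measure turnaround.

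Most of this stands, and it limits the consequence. It does not remove the gap. Concern about potassium explains a draw at 4.5 h, but not why that draw omits analytes that lower-risk patients have measured at about 4 h. Discretionary labs and clinical observation supplement a required minimum; they do not explain why the minimum is thinner in the higher-risk tier. The 4-hourly instruction could be read as starting at end of infusion, but the explicit bullets place only a potassium there. If a full panel was intended, the wording still needs correcting.

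**Conclusion.** The concern holds. When TLS is not already evident, the first required full panel after baseline comes at about 8.5 h (8.1 to 8.9 h) in high-risk patients and about 4 h in the others. This result rests only on the stated durations and schedules, and it holds across the permitted infusion windows.

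The mean-wait comparison (4.25 h against 2.10 h) also needs uniform onset over 0 to 8.5 h and is illustrative. The whole excess falls on abnormalities that begin during the bolus and infusion. Potassium is measured at nearly the same times in both tiers.

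This is a gap in required safety monitoring. It does not touch the potassium treatment triggers, and because the SAP's laboratory TLS window runs to 7 days after the start of study drug, any effect on reported TLS rates is likely negligible. The change is still worth making: it is cheap and concerns the patients in whom TLS is most expected.

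**What to change.** Make two wording changes in the high-risk part of Protocol 4.4.1.1.

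1. At end of infusion, require a STAT full TLS panel in place of the STAT potassium. The blood draw is the same. The first full panel moves from about 8.5 h to about 4.5 h (4.1 to 4.9 h).
2. State that all TLS labs in the first 24 hours after the end of infusion are run STAT, matching the rule already written for the lower tier.

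The rest of the schedule can stay, including the 2-hour potassium and the step-up.

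The cost is one full panel in place of one potassium assay, plus STAT handling of the 6 panels already scheduled from 8.5 to 28.5 h (11 if they are 2-hourly). The drawback is a heavier STAT load on the laboratory. No extra blood draw or visit is needed, because these patients are already hospitalised.

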4.4.1.2 Diarrhea

If diarrhea occurs during therapy, patients should initiate loperamide (or equivalent) 2 mg by mouth every 2 hours during the waking hours. The rapid introduction of loperamide (or equivalent) at the first signs of diarrhea is strongly encouraged. Once the diarrhea is controlled, the time interval of loperamide may be titrated to a frequency that adequately controls the diarrhea. The diarrhea observed with alvocidib almost always resolves following completion of therapy, so treatment with loperamide following completion of therapy will not be required in most patients. If loperamide (or equivalent) does not control diarrhea, cholestyramine (or equivalent) 5 gm orally four (4) times daily may be added. For patients developing diarrhea during alvocidib administration, subsequent treatments should include a similar diarrhea prophylaxis. If diarrhea is not controlled with the above prophylactic regimen and is grade 2 or greater, therapy should be held until diarrhea has resolved. Replacement of excessive fluid losses should be done unless otherwise clinically indicated.

4.4.1.3 Nausea/Vomiting

Antiemetics (ie, 5-hydroxytryptamine [5-HT₃] receptor inhibitor or other antiemetic medications) are permitted according to standard practices at each investigational site.

4.4.1.4 Infection Prevention

Prophylactic antibiotics including levofloxacin (or equivalent) 500 mg orally once daily and valacyclovir (or equivalent) 500 mg orally BID each day should be administered at the start of chemotherapy. Alternative prophylactic antibiotic or antiviral therapy is left to the discretion of the treating physician and according to institutional standards.

Antifungal prophylaxis to be administered according to each institution's standard of care.

Routine growth factor support is not allowed ≤Day 35 unless otherwise discussed with the Medical Monitor. Growth factor support can be given at the discretion of the Investigator >Day 35 of Induction/Reinduction therapy in the presence of life-threatening infection with ongoing neutropenia. Growth factor support during Consolidation therapy may be administered according to each institution's standard of care.

4.4.2 Management of Hematologic Toxicities

Adverse events that are moderate to severe in intensity (see [Appendix C](#) for toxicity grading) and considered possibly or probably related to study drug treatments may result in the termination of study treatment in the affected study patient. Such termination should be reviewed with the Sponsor's Medical Monitor at the earliest possible time (see [Section 8.5](#)). Following review with the Sponsor's Medical Monitor, the study patient may be permanently withdrawn from the study depending upon the nature and severity of the event.

Adverse events may be treated with concomitant medications, as deemed clinically indicated by the Principal Investigator. All concomitant medications must be recorded on the appropriate CRF.

4.4.3 Dose-limiting Toxicities

Dose-limiting toxicities (DLTs) for alvocidib and 7+3 will be determined during **Induction and Reinduction** therapy, determined to be at least possibly related to study drug and defined as follows based on the NCI CTCAE version 4.03:

- Any Grade 4 nonhematologic toxicity considered at least possibly drug related
- Any Grade 3 nonhematologic toxicity considered at least possibly drug related and that does not resolve to ≤Grade 2 within 48 hours, with the following exceptions:
 - Grade 3 diarrhea, mucositis, nausea or vomiting will be considered dose-limiting only if resolution to <Grade 2 (including use of supportive care) requires more than 7 days
- Grade 4 cytopenias lasting ≥50 days from the start of the cycle in the absence of residual leukemia if subject received one cycle of induction

- Grade 4 cytopenias lasting ≥ 60 days in the absence of residual leukemia if subject received 2 cycles of induction
- Grade 3 or 4 tumor lysis syndrome or related electrolyte disturbances (eg, hyperkalemia, hypophosphatemia, hyperuricemia) that do not resolve to \leq Grade 2 within 14 days
- \geq Grade 3 elevations in creatinine that do not resolve to \leq Grade 2 within 7 days
- Any AST and ALT elevation $\geq 5 \times$ ULN accompanied by serum bilirubin levels $> 2 \times$ ULN, regardless of duration
- Any Grade 5 toxicity that is not clearly and incontrovertibly related to the underlying disease or extraneous causes
- Anorexia, alopecia, fever, neutropenic fever, and infections of any grade should not be designated as DLTs since they are known and expected toxicities associated with the study drugs.

4.4.4 Dose Modifications

During Induction/Reinduction, there will be no dose reductions for alvocidib or cytarabine. Unless an elevation in total bilirubin level is secondary to suspected Gilbert syndrome, hemolysis (as reflected by an increase in indirect bilirubin level), or hepatic leukemic infiltration, the dose of daunorubicin must be reduced by 25% per day per dose if the patient's total direct bilirubin value is ≥ 1.2 mg/dL and ≤ 3 mg/dL, and must be reduced 50% per day per dose if the patient's total direct bilirubin value is > 3 mg/dL on the day of planned daunorubicin administration. Bilirubin adjustment should be based on direct measurement. Patients with serum creatinine concentrations > 3 mg/dL should receive 50% of the planned dose. Daunorubicin must be omitted from subsequent cycles if the patient's lifetime daunorubicin equivalent exceeds 460 mg/m² (see [Appendix G](#) for conversion table) or their left ventricular ejection fraction (LVEF) drops below 45%.

The HiDAC dose may be modified during Consolidation at the discretion Investigator.

